If the toxicities requiring dose reduction as defined above do not recover based on the criteria defined in [Table 6](#) through [Table 8](#) within the 21 days of the last dose of TAS-120, the patient

will be discontinued permanently from the study. If resumption criteria are met within 21 days of the last dose of TAS-120, the patient can resume TAS-120 treatment at the appropriate dose level according to instructions provided in [Section 9.1.3.1](#), TAS-120 Dose Reductions for Treatment-emergent Toxicities.

Treatment-emergent toxicities should be followed until stabilization according to [Table 9](#).

Table 9: Required Follow-up for Toxicities

Toxicity	Follow-up evaluation
Hematology	If \geq CTCAE grade 3 neutropenia or \geq CTCAE grade 3 thrombocytopenia have been demonstrated, these parameters must be repeated at least twice a week until resolution to \leq CTCAE grade 1 or baseline to allow for initiation of re-treatment, and then at least weekly until either initiation of retreatment or until stabilization.
Renal	If creatinine clearance (calculated* or measured value**) < 30 mL/min has been demonstrated, this parameter must be repeated at least twice a week until resolution to baseline to allow for initiation of re-treatment, and then at least weekly until either initiation of re-treatment or until stabilization.
Hepatic	If bilirubin ≥ 2 x ULN or \geq CTCAE grade 3 ALT or AST or the combination of \geq CTCAE grade 2 bilirubin and \geq CTCAE grade 2 ALT or AST elevation has been demonstrated, these parameters must be repeated at least twice a week until resolution to \leq CTCAE grade 1 or baseline to allow for initiation of re-treatment, and then at least weekly until either initiation of re-treatment or until stabilization. Patients with total bilirubin $> 1.5 \times$ ULN, or > 3.0 mg/dL for patients with Gilbert's syndrome (any duration) should have fractionation of bilirubin into total/direct or indirect/direct components and any additional work-up as clinically indicated by these results. Follow-up of hyperbilirubinemia should proceed as per the guidelines above, irrespective of the results of fractionation.

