9.16. Adverse Event Assessment

Patients will be monitored for any untoward medical events (AEs or SAEs) from the time the main study ICF is signed through 30 days after last dose of TAS-120 or until the start of new antitumor therapy, whichever is earlier. For the Phase 2 part of the study, any AEs or SAEs that occur after the signing of pre-screening consent and are directly associated with a pre-screening procedure (i.e., fresh tumor biopsy) should be reported as described in Section 12.1. For AEs and SAEs that occur between signing the pre-screening consent and main study ICF, there is no need to record those that are unrelated unless it is mandatory by local regulations.

Serious AEs should be reported to Taiho Oncology, Incorporated (TOI) Pharmacovigilance or its designee. If serious medical occurrences or deaths **outside** the 30-day follow-up period are

reported to or observed by the investigator that he/she believes are related to the administration of the TAS-120, it is the investigator's responsibility to report this occurrence to TOI Pharmacovigilance or its designee. See [Section 11.1.1](#), Adverse Events, and [Section 11.1.2](#), Serious Adverse Events, for definitions and detailed reporting of AEs and SAEs.

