9.21. Survival Status Follow-up

Overall survival status will be collected during the survival follow-up period every 3 months (± 2 weeks) from the patient's previous visit.

For the Phase 1 Expansion part of the study, patients should be followed for up to 12 months after the last patient enrolled in this phase of the study.

For Phase 2, patients should be followed for up to 18 months after the last patient enrolled in this part of the study.

CCI

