All AEs will be reported from the time the main study ICF is signed through the period of patient follow-up (30 days after the last dose of study drug or until the start of new antitumor therapy, whichever is earlier). For the Phase 2 part of the study, any AEs that occur after the signing of pre-screening consent and are directly associated with a pre-screening procedure (i.e., fresh tumor biopsy) should be reported. For AEs that occur between signing the pre-screening consent and main study ICF, there is no need to record those that are unrelated unless it is mandatory by local regulations. All AEs will be documented in the eCRF. Documentation should include onset and resolution/stabilization dates, severity/grade, relationship to study drug, and outcome of the event. All AEs should be entered in the eCRF within 10 business days from the time the investigator first becomes aware of the AE.

Causal relationship is assessed based on the following:

1. Select “Related” if the event follows a reasonable temporal sequence from administration of study medication and at least **one** of the following conditions is true:
 - A positive dechallenge: This means that the event improves or resolves after the drug is stopped (temporarily or permanently).
 - A positive rechallenge: This means that the event reappears after the drug is restarted.
 - The event cannot be reasonably explained by the patient’s clinical state and/or other therapies administered.

The circumstance that a causal relationship can sometimes not be ruled out is not sufficient to determine that the event is “related”. Instead, “related” should mean that there is evidence to suggest a causal relationship between the drug and the AE. A reasonable possibility is provided by the following example that would suggest a causal relationship between drug and the event: A single occurrence of an event that is uncommon and known to be strongly associated with drug exposure (e.g., angioedema, Stevens-Johnson syndrome).

2. Select “Not related” if there is no **reasonable** possibility that the study medication caused the event, or if the event does not follow a reasonable temporal sequence from administration of study medication and could have been produced by a documented pre-existing condition, concomitant medication or patient’s clinical state. For the purposes of safety reporting, “no reasonable possibility” means there is no evidence to suggest a causal relationship between the drug and the AE.

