Any ongoing AEs should be followed until the earliest occurrence of one of the following:

- AE has resolved.
- AE has stabilized.
- The AE reporting process is provided in the eCRF Completion Guidelines.

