11.2.2. Repeat Testing

Evaluation of any clinically significant laboratory test will be repeated, as clinically indicated, until the value returns to the baseline level or clinically stabilizes, or until new anticancer treatment, surgery, or radiotherapy is given.

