#### 7.5. Time-to-Resolution Definition

In order to derive the time-to-resolution, overlapping or contiguous AESI within a specific category will be collapsed into what will be termed "clustered" AESI. For example, if a subject (without pre-treatment AE) experienced an AE from 01 January to 05 January, another AE (with different PT but within same category) from 06 January to 11 January, and the same AE from 10 January to 12 January, these will be collapsed into one clustered AESI from 01 January to 12 January. Table 13 summarizes key derivation steps for each type of clustered select AEs. Algorithm for collapsing multiple records of adverse event is summarized in Section 7.6.

Time-to-resolution of AESI (any grade) for a specific category is defined as the longest time from onset to complete resolution or improvement to the grade at baseline among all clustered AESI in this category experienced by the patient. Events which worsened into Grade 5 events (death) or have a resolution date equal to the date of death are considered unresolved. If a clustered AESI is considered to be unresolved, the resolution date will be censored to the last known date alive. Improvement to the grade at baseline implies that all different AE events in the clustered AESI should at least have improved to the corresponding (that is, with same preferred term) baseline grade. This measure is defined only for subjects who experienced at least one AESI in the specific category.

The time-to-resolution of AESI (Grade 3-5) for a specific category is defined similarly with an onset date corresponding to a Grade 3-5 AESI.

Time-to-resolution of study treatment-related AESI (any grade or Grade 3-5) is defined similarly but restricted to study treatment-related AESI.

Time-to-resolution for a specific subcategory is defined similarly but restricted to events of this subcategory.

**Table 13.** Derivation of Clustered AESI

Type of clustered select AE	Derivation
Any grade	Collapse any on-treatment AESI from the same category
Study treatment-related of any grade	Collapse any on-treatment, study treatment-related AESI from the same category
Grade 3-5	Collapse any on-treatment AESI from the same category. Resolution will be based on the onset date of the earliest Grade 3-5 records (if no Grade 3-5 record, clustered AESI is excluded)

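### Unresolved AESIs are censored at the date last known alive, so for patients who stopped treatment with an event open, time after AE observation ended can be counted as still unresolved

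*SAP*

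**What the plan says.** Phase 2 SAP 7.5 defines time to resolution on clustered AESIs and gives one censoring rule: "If a clustered AESI is considered to be unresolved, the resolution date will be censored to the last known date alive". Expansion SAP 8.5 repeats it. Neither section limits the date to the last AE assessment or to data cut-off. SAP section 6.5.2.6 (Phase 2 and Expansion) plans a Kaplan-Meier median with 95% CI for selected AESIs, hyperphosphatemia included.

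The protocol's collection rules run on different clocks:

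- **AE monitoring** (9.16) runs "through 30 days after last dose of TAS-120 or until the start of new antitumor therapy, whichever is earlier".
- **AEs already open** (11.1.1): "Any ongoing AEs should be followed until the earliest occurrence of one of the following". One of these endpoints is resolution and another is "AE has stabilized". This rule has no day-30 stop.
- **Repeat laboratory tests** (11.2.2) continue "until the value returns to the baseline level or clinically stabilizes, or until new anticancer treatment, surgery, or radiotherapy is given".
- **Survival** (9.21): "Overall survival status will be collected during the survival follow-up period every 3 months", for up to 18 months after the last Phase 2 enrolment.

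The neighbouring time-to-onset rule (Phase 2 SAP 7.4) is tighter. It stops follow-up at last dose + 30 days for off-treatment patients followed at least that long, and uses the date last known alive only otherwise.

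**The concern.** A Kaplan-Meier estimate assumes that a patient in the risk set would be seen to have the event if it occurred. A survival contact shows that the patient is alive. It does not show whether phosphorus has returned to baseline. In the Phase 2 schedule (Protocol Table 2), the survival follow-up column holds only survival status and, conditionally, tumor scans. It has no chemistry and no AE assessment.

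A patient who starts new therapy with the event open can therefore be carried for months as unresolved without being observed. The denominators stay too large, the resolution curve rises too slowly, and the distortion depends on how long patients live rather than on how long the toxicity lasts. At stake is the reported median time to resolution, and any resolution rate read from the curve, for hyperphosphatemia and the other AESIs.

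**Working it through.** The plan gives no figure for this analysis, so there is none to reproduce. The check sets the rules side by side and then illustrates the effect on assumed inputs.

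**Step 1. When the two dates separate.**

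| Patient with an open AESI | End of AE or laboratory observation | Date last known alive |
|---|---|---|
| Still on treatment | latest visit (chemistry every 21-day cycle) | about the same |
| Dies within the AE window | near death | about the same |
| Off treatment, event still followed under 11.1.1 | latest AE assessment | same or somewhat later |
| Off treatment, new therapy started | AE monitoring and repeat laboratory tests may end there | later, moved by 3-monthly contacts |
| Event closed as stabilized | date of closure | later, moved by 3-monthly contacts |

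The rule matters only in the rows where the last column runs past the middle one.

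**Step 2. Direction.** Each resolution multiplies the estimated unresolved fraction by (1 − 1/n), where n is the number at risk. Patients who cannot be seen to resolve inflate n, so each step is too small. If loss of observation is unrelated to resolution, the bias is always toward longer times.

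**Step 3. Size if observation stops around last dose + 30 days.** None of these inputs is in the documents. Assumed, all exponential: median onset to last dose 3 or 6 months; post-treatment survival median 9 months, capped at 18; a given share of patients has observation stop at last dose + 30 days. There were 200,000 simulated patients per scenario.

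| True median (months) | 25% stopped | 50% stopped | 100% stopped |
|---|---|---|---|
| 1 | 1.0 | 1.0 | 1.0 |
| 3 | 3.1 | 3.1 to 3.3 | 3.3 to 3.8 |
| 6 | 6.4 to 6.7 | 6.8 to 7.9 | 8.8 to not reached |

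With 0% stopped there is no bias. Censoring at the end of observation returns 1.0, 3.0 and 6.0 within simulation error. Rates can move when the median does not: for a true median of 1 month and 100% stopped, the 6-month resolution rate is 88% to 93% against a true 98%.

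In days, with the same structure and 30% to 50% stopped, a true median of 60 is reported as at most about 62, and a true 90 as about 92 to 98.

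**Step 4. Size if observation is lost early.** Assume instead that 30% to 50% of patients lose AE observation 10 to 60 days after onset and are last known alive at days 200 to 700. A true median of 60 days is then reported as about 74 (30% lost) or 98 (50% lost). The 90-day rate is 55% or 48%, against 1 − 2^(−90/60) = 65%.

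**Step 5. When the loss is closure as stabilized.** Assume 70% of events resolve with a median of 30 days and 30% stabilize, with follow-up closed at days 10 to 60.

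- Stabilized events never resolve: true 90-day rate = 0.70 × (1 − 2^(−90/30)) = 0.70 × 0.875 = 61%. The SAP rule gives 61%. Censoring at closure gives 81%.
- Stabilized events resolve with a median of 365 days: true rate = 61.25% + 0.30 × (1 − 2^(−90/365)) = 61.25% + 0.30 × 15.7% = 66%. The SAP rule gives 63%. Censoring at closure gives 82%.

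For this group the present rule is close to the truth, and censoring at closure is far too optimistic.

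**The case against.** The strongest defence has four parts.

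1. *AE follow-up does not simply end at day 30.* A reader might infer from 9.16 that everything after last dose + 30 days is unobserved. The documents do not support that. The 30-day limit governs which AEs are reported; an AE already open is followed until it resolves or stabilizes, and toxicities likewise ("Treatment-emergent toxicities should be followed until stabilization according to" Table 9, in Protocol 8.1.3.1.2). This stands, and it confines the problem to the rows picked out in Step 1.

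2. *A large bias needs inputs that the documents do not give.* A reader might take Step 4 as the expected effect. It requires many patients to lose observation within about two months of onset. Patients on treatment have chemistry every cycle, at end of treatment and at the 30-day visit. For hyperphosphatemia, the one AESI named, Protocol Table 7 keeps Grade 1 and 2 patients on drug and starts with dose reduction at Grade 3. This also stands: Step 4 is a stress case.

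3. *Censoring at the last assessment is not always better.* Step 5 shows that this is right for events closed as stabilized, and it shapes the fix.

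4. *The consequence is limited.* The analysis is descriptive and single-arm, with no decision rule. The percentage of patients whose longest AESI resolved is reported alongside and does not depend on the censoring date. When the rule errs in the way described, it overstates persistence, the cautious direction for safety. This is true, but it does not make the median correct.

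**Conclusion.** The point holds in a limited form. Both SAPs use a date driven by survival contact to censor an endpoint that can be observed only through AE or laboratory follow-up. For patients who leave treatment with an event open, the gap can be months, and the estimate is then biased toward slower resolution. The inconsistency with the SAP's own time-to-onset rule suggests oversight rather than intent.

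The size cannot be derived from the documents. It depends on the speed of resolution, the share of open events whose observation stops, and when it stops. It is nil or small when resolution is fast or observation ends around last dose + 30 days. It becomes material with slow resolution (a true median of 6 months and half stopped gives 6.8 to 7.9) or with heavy early loss. Steps 2 to 4 assume that loss is unrelated to resolution; Step 5 shows the conclusion changes when it is not. No efficacy result is touched.

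**What to change.** In Phase 2 SAP 7.5 and Expansion SAP 8.5, replace the censoring date for unresolved clustered AESIs with the last date on which the event's status was assessed, from the AE record or the relevant laboratory value, and no later than data cut-off. Keep Grade 5 events and events open at death as unresolved, as now.

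Add a sentence for events closed as stabilized: either keep them as unresolved to the date last known alive, or report the result both ways. Protocol 11.1.1 already asks for the resolution or stabilization date and the outcome, so these events should be identifiable.

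Do not use last dose + 30 days as a fallback date unless resolutions after that date are excluded too. Otherwise later resolutions count as events while unresolved patients are cut off at day 30, which favours fast resolution.

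The cost is a sentence or two and one derivation in each SAP, with no new data collection. The downside is shorter censoring times and slightly less follow-up for some unresolved events.

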# 7.6. Multiple Adverse Events

The algorithm for collapsing multiple records of select adverse event is using the following conventions. For each patient and specified category, the corresponding adverse event records will be collapsed when:

Multiple adverse event records have the same onset date.

The onset date of an event record is either the same day or 1 day later than the resolution date of a preceding event record (contiguous events).

The onset date of an event record is after the onset date and prior to or on the resolution date of a preceding event record (overlapping events).

# 7.7. Other Data Handling Rules

Missing data will not be imputed in the patient level listings. The listings will only present the data recorded on the original CRF.

If an AE has a completely missing onset date, then the AE will be considered a TEAE. A medication with a completely missing start date is considered a prior medication. A medication with a completely missing stop date is considered a concomitant medication.

Taiho Oncology, Inc. Statistical Analysis Plan (Phase 2) – Protocol TPU-TAS120-101

15 October 2020

If an adverse event or a medication has a partial missing start or stop date, the following rules will be used to determine whether it is an AE or a TEAE, or a prior or concomitant medication.

Table 14. Partial Date Imputation Rule for TEAE or Medication

Partial Missing Start or	Derived Start Date	Imputed Stop Date	
Stop Date			
Missing month and day,	January 1 of that year or first dose	December 31 of that	
and the year is present	date if the year is the same as the	year	
	year of first dose date		
Missing day, but year and	First day of that month or first	Last day of that month	
month are present	dose date if the year and month are		
	the same as the year and month of		
	first dose date		
Missing month, but year	Missing month derived as January	Missing month imputed	
and day are present	or same as first dose month if the	as December	
	year is same as the year of first		
	dose.		

The rule above in Table 14 is also used for determining the cycles of adverse events and concomitant medications.

The derived date is only used for determining TEAEs, cycle of adverse events and concomitant medications. The collected partial dates will be reported in the listings.

For the medical history, prior surgery, prior radiotherapy, and prior systemic cancer therapies:

- Missing day and month January 1 will be assigned to the missing fields.
- Missing month only Treat day as missing and replace both month and day according to the above procedure.
- Missing day only Assign first of the month to the missing day.

Partially missing stop dates for the types of data listed above will be imputed as:

- year is missing, no imputation. Date left missing.
- month is missing and year is prior to year of first dose of study medication- impute 'December'.
- month is missing and year the same as the year of the first dose of study medication impute same month as in start date of study medication.
- day is missing, impute 'last date of that month'. If results in a date ≥ the date of the first dose of study medication impute day as the day prior to the first dose of study medication.

# 9. REVISION HISTORY

Table 15: List of changes from Version 1.0

Section	Changes from Version 1.0	Revision Rationale
5.4	Section 5.4 Timing of Analysis is added as a new section: The final analysis for primary objective will be performed when majority of treated patients responding to futibatinib had at least 6 months of follow-up from onset of response.	The timing for analysis is added per FDA's requirement for a complete package including efficacy data for all patients enrolled in this study and ensure that the majority of patients have sufficient follow up (i.e., a minimum of 6 months from onset of response) for the NDA submission
6.4.2	'Liver lesions only vs. lesions in and outside of liver' is removed from subgroup analysis	This information was not collected in the EDC per CRF design.
6.4.2	
 
The following subgroup analysis is added:
 
Prior (neo) adjuvant treatment (Yes, No)
 
Baseline FGFR rearrangements status by local lab (commercial test provided to clinician as standard of care based on tumor tissue) and/or central lab (clinical trial assay performed on tumor tissue)
 
Patients with solid tissue sample and report
 
	(neo) Adjuvant is a relevant subgroup of interest Biomarker test subgroup analysis are added per FDA CDx request
6.5.2.5	Add additional analysis of Hyperphosphatemia toxicities based on CTCAE v5.0 criteria (Table 9)	To have a comprehensive assessment of hyperphosphatemia, analysis based on both CTCAE v5.0 criteria and protocol specified criteria will be performed.
6.5.3	Liver toxicity analysis are added.  The number of subjects with the following laboratory abnormalities from on-treatment evaluations will be summarized	Revised per the FDA's recommendation to include liver toxicity analysis.

• ALT or AST $>$ 3 x ULN, $>$ 5 x ULN, $>$ 10
x ULN and $> 20$ $x$ ULN

- Total bilirubin > 2 x ULN
- Concurrent (within 1 day) ALT or AST > 3 x ULN and total bilirubin > 2 x ULN
- Concurrent (within 30 days) ALT or AST > 3 x ULN and total bilirubin > 2 x ULN

The following scatterplots will be produced for the following hepatic laboratory parameters:

- Total bilirubin peak vs. AST peak
- Total bilirubin peak vs. ALT peak

On-treatment peak total bilirubin and ontreatment peak AST/ALT may or may not happen on the same day of liver testing.

A by-subject listing of these specific abnormalities will be provided.

